# e. Screening method:

Subjects will be screened by FBC, ESR, CRP, Coeliac serology following Rome III criteria for diagnosis of IBS.

### f. Eligibility:

### g. Inclusion Criteria:

- 1. Diagnosed case of IBS using Rome III criteria
- 2. Absence of red flag sign: anemia, fever, wt loss, per rectal bleeding, nocturnal frequency, family history of IBD, cancer
- 3. Age 18-55 years
- 4. No probiotics used in prior 3 months.
- **5.** Agreed not to start any other drug unless clinically indicated.
- **6.** No antibiotics in previous 2 months of enrolment.

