# **PROTOCOL**

Supplementation with a multi-strain probiotic formulation (Bio-Kult®) in the management of diarrhoea-predominant irritable bowel syndrome - a randomized, double-blind, placebo-controlled clinical trial

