#### **ABSTRACT**

**Background:** Irritable Bowel Syndrome (IBS) is a common functional gastrointestinal disorder. Common clinical manifestation include abdominal pain, bloating, altered bowel habit which bears a great impact on the quality of life of an individual. Previously limited number of studies carried out in our country to assess the effect of probiotics on IBS patients which yielded mixed results. Further study preferably with larger sample and longer duration was recommended. Aims and objectives: This study aims to see the effect of probiotics on IBS.

Material and method: This is a controlled randomized clinical trial. The patient will be selected on the basis of Rome III criteria. IBS patients with a sample size of 400 will be taken. Purposive non probability method of sampling will be employed. In this method the patients who will be readily available and in close proximity will be selected according to the selection criteria. Patient will be collected from gastroenterology outpatient department. After full explanation of the study procedure, informed written consent will be taken. Participants will be randomized to receive either probiotics (Biocult®, Sandooz Bd. Ltd.) with standard treatment or only standard treatment for 8 weeks. All participants will be interviewed with baseline symptom score. Similar interview for symptom score will take place at 1 month interval for 3 times (including 1 month post treatment). All data will be processed by the SPSS program values will be expressed as frequencies or mean±SD unless otherwise mentioned. Between groups analysis will be done by Chi-square test, unpaired or paired students t-test as applicable; while predictive values will be seen by regression analysis. Only P values <0.05 will be considered as significant.

**Result:** This study will see the effect of two months use of probiotics on IBS and thereby highlight over the longer treatment of IBS.

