#### RATIONALE OF THE STUDY

Many drugs have been advocated in the treatment of IBS, for instance, spasmolytics, bulking agents, psychotropic agents, and 5-HT receptor antagonists. However, in many cases all these options remain disappointing for the relief of symptoms. The therapeutic efficacy in IBS is probably impacted by the heterogeneous pathogenesis of the disease which includes altered intestinal motility, visceral hypersensitivity, abnormal brain gut interaction, food intolerance, altered intestinal permeability and post infectious changes. Recently, the adverse role of alteration of gut micro flora at the onset of symptoms has been emphasized. Therefore, rationale exists for the therapeutic use of probiotics in IBS. In 2004-2005 a randomized, double blind placebo controlled trial (Kabir MA et al, 2011) on the effect of S. boulardii in diarrhea predominant IBS patients was conducted at BSMMU but the result was not satisfactory. Another study (Rahman MZ et al, 2013) at BSMMU during 2010-2011 with multistrain probiotics yielded a beneficial outcome which was significant both clinically and statistically. On both occasions, further study was suggested preferably with a larger sample size. These recommendations for further study prompted this study to be carried out in order to assess the effect of multistrain probiotics in relation to change of symptom scores in IBS patients and also to see changes of quality of life before and after the treatment. As per EMEA guideline, previous study (Spiegel B et al, 2009) revealed that abdominal pain is the most prevalent and distressing symptom in IBS patients and changes in the severity of pain were reflected as a more reliable outcome of successful treatment. IBS shouldn't be diagnosed in the absence of abdominal pain or discomfort. The pain or discomfort is typically relieved by

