defecation or its onset is associated with an increased or decreased frequency of stool or looser or harder stool. The pain often is poorly localized, waxes and wanes, may be aggravated by eating & can occur in any part of abdomen; although it is more typically located in the lower abdomen. It can be referred to different areas in the abdomen or to the chest or back. Exacerbation of pain by stressful life events or difficult life situation is common. As abdominal pain is the hallmark feature of IBS and is recommended for the time being to assess the main symptomatology in at least partially validated scale. So, improvement of abdominal pain or discomfort along with abnormalities in defecation is considered as primary outcome. For other subtypes of IBS, and for "global" development programs intending to treat two or more subtypes, the use of the global assessment is, however, still recommended. Both endpoints should be evaluated as responder rates. The numerical evaluation of changes in scales is regarded to be a secondary endpoint. As per EMEA Guidance on The Evaluation of Medicinal Products for the Treatment of IBS, a responder has to demonstrate abdominal pain score which has improved at least 30% compared to baseline. Recent studies also show that there is high placebo response rate in functional bowel disorders which has a negative correlation with duration of study. So to overcome this confusion of high placebo response, this study is designed, unlike previous studies in our country, with a longer study period along with a larger sample size.

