# RESEARCH QUESTION

Is multistrain probiotics with standard treatment more effective at reducing IBS symptoms than standard treatment of IBS?

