# **OBJECTIVES OF THE STUDY**

# **Primary Objectives:**

- To assess the effect of multistrain probiotics on abdominal pain using a validated symptom severity score in IBS patients.
- 2. To assess the efficacy of a multi-strain probiotic supplement as a treatment option for IBS in a tertiary referral centre

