# **Secondary Objectives:**

- To assess the effect of probiotics on global symptom severity scores which includes other symptoms of IBS (stool consistency, frequency, bloating) using a validated symptom severity score.
- 2. To assess changes in the use of rescue medication (i.e. laxatives or anti diarrhea medication such as Loperamide).
- 3. To assess any adverse events reported with probiotic use.

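### The title restricts the trial to diarrhoea-predominant IBS, but nothing in the eligibility criteria, definition or entry rule shown does, so a mixed-subtype population could be randomised and reported as diarrhoea-predominant IBS

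*Protocol*

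**What the plan says.** The title describes a trial of the probiotic "in the management of diarrhoea-predominant irritable bowel syndrome". The rest of the protocol drops that restriction:

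- Abstract: "IBS patients with a sample size of 400 will be taken", selected on Rome III criteria.
- Research question: whether the probiotic with standard treatment is "more effective at reducing IBS symptoms than standard treatment of IBS".
- Primary Objectives: the probiotic is assessed "as a treatment option for IBS in a tertiary referral centre".
- Section g (Inclusion Criteria), item 1: "Diagnosed case of IBS using Rome III criteria". Section a (Study Population) says the same in nearly the same words.
- Secondary Objectives: rescue medication is given as "laxatives or anti diarrhea medication such as Loperamide".

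In the text shown, the subtype term occurs in only two other places: the Rationale, where an earlier trial on the "effect of S. boulardii in diarrhea predominant IBS patients was conducted at BSMMU" is described, and that trial's entry in the References. Neither describes the present trial.

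**The concern.** The title and the operative text name different populations, and the difference decides either who is enrolled or what may be concluded. If the title states the intention, no rule shown keeps other subtypes out. If the body states it, a result from IBS of any subtype would carry a title that attributes it to one subtype.

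The endpoint is affected too. The Rationale makes abdominal pain with abnormal defecation the primary outcome. It then remarks that a global assessment remains recommended for other subtypes and for programmes covering two or more. The objectives put pain first and the global score second. Whether that order agrees with the protocol's own reasoning cannot be judged until the population is settled.

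Later repair may not be possible. Item 6 of the data collection sheet asks what form motions ever take and allows several answers, so it does not grade which pattern predominates. No rule shown uses the answers to assign a subtype.

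**Working it through.** The question is mainly one of text, so the check asks of each place whether it limits the trial to one subtype.

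| Place in the protocol | Population or rule | Limits subtype? |
|---|---|---|
| Title | Diarrhoea-predominant IBS | Yes |
| Abstract | 400 IBS patients, Rome III | No |
| Research question | IBS | No |
| Primary Objectives | IBS | No |
| a. Study Population | Rome III IBS | No |
| e. Screening method | Blood tests and coeliac serology, Rome III diagnosis | No |
| g. Inclusion Criteria | 6 criteria | 0 of 6 |
| h. Exclusion Criteria | 6 criteria; the bowel-related ones are organic disease and previous surgery | 0 of 6 |
| j. Operational definition | Pain or discomfort plus at least two of three features | No |
| Procedures of preparing and organizing materials | All who meet the inclusion criteria and no exclusion criterion are entered | No |

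**Eligibility count.** 0 of 6 + 0 of 6 = 0 of 12 criteria name a subtype.

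**Definition.** The three features are relief with defecation, a change in stool frequency and a change in stool form. None gives a direction. The Rationale describes IBS in both directions: "its onset is associated with an increased or decreased frequency of stool or looser or harder stool". A patient with harder, less frequent stools can therefore meet the definition.

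**Entry rule.** The Procedures section makes the listed criteria decisive, so such a patient is included if no exclusion applies.

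**Size.** The protocol gives no subtype share. The criteria allow from 0 to 400 of the 400 participants to be outside the titled population. This is what the text permits, not a forecast.

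**Sample size, for completeness.** The stated figure reproduces: 2 × 87.77² × (0.84 + 1.96)² / 30² = 134.2, rounded up to 135 per group and 270 in total. The adjustment gives 270 / (1 − 0.08 − 0.08)² = 382.7 against the stated 384, which is rounded to 400. Nothing here turns on that small difference.

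**Illustration only.** Suppose the conclusion were to be drawn for diarrhoea-predominant patients alone. The share of such patients is my assumption. The difference of 30 (used as points, as the protocol's formula does) and the SD of 87.77 are the protocol's. With n = 200 × share per group and no dropout, power = Φ(30 / (87.77 × √(2/n)) − 1.96):

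| Assumed share | n per group | Power |
|---|---|---|
| 25% | 50 | 40% |
| 50% | 100 | 68% |
| 75% | 150 | 84% |
| 100% | 200 | 93% |

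The protocol's own 135 per group is 135/200 = 67.5% of those randomised. Below roughly that share, the subtype alone would have less than 80% power, before any dropout. The finding does not depend on these figures.

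**The case against.** The strongest reply is that the body is consistent with itself and the title is the outlier. Recruiters have one workable rule and would not face two competing criteria. The title also departs from the body elsewhere: it says double-blind and placebo-controlled, while the Abstract and Procedures give the comparison group standard treatment only (although section i, Sample Size, does mention placebo). On this view the defect is one adjective, and enrolling all subtypes is a legitimate design. That may be the right reading, but it does not remove the defect. The title would then misstate the population and need correcting.

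A second reply is that not everything is visible. The flow chart is not shown, the extracted data sheet runs from item 2a to item 6, and the Rome III questionnaire is not reproduced. So whether some form records the predominant stool pattern is unknown. This limits what can be said about data collection. It does not affect eligibility, because the two criteria lists are intact and the entry sentence relies on them alone.

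Third, some of the supporting evidence is weak. Laxatives are named only as examples of medication, and a symptom sheet covering all stool forms suits either population. I accept that, and the conclusion does not rest on either. I also accept that a range of 0 to 400 says little beyond the absence of a restriction.

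Deferring the matter to a statistical analysis plan would not help. Such a plan can define analysis sets but cannot change whom the protocol admits.

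**Conclusion.** The concern holds. In the text shown, the title is the only statement that limits this trial to diarrhoea-predominant IBS, and the rules that govern entry admit IBS of any subtype. The protocol does not show which was intended. The conclusion is that a mixed population could be randomised and reported under the narrower label, not that one was. How many participants would be affected cannot be estimated from the document. Because the point decides who is in the trial or what it may claim, it must be settled before enrolment. It does not call the stated sample size into question.

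**What to change.** Reconcile the title, Abstract, Research question, Primary Objectives, sections a, g and j, and the entry rule under Procedures. Include the Rationale's remark on endpoints for other or multiple subtypes. There are two ways, and the choice is the sponsor's.

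- **If the title is intended:** add an explicit diarrhoea-predominant criterion to sections a and g, put its definition in section j, and record the predominant stool pattern at baseline if no existing form does so. This costs one eligibility line, one definition and at most one data item. The downside is slower recruitment within the 12 months of data collection in the time table.
- **If all subtypes are intended:** remove the subtype from the title, limit conclusions to IBS overall, and state how the order of the pain and global endpoints fits the Rationale's remark. This costs a title edit and a few sentences. The downside is a broader, more heterogeneous claim.

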#### h. Exclusion Criteria:

- 1. Age<18 or >55 years
- 2. Previous treatment with probiotics within last 3 months
- 3. Pregnant or lactating lady
- 4. Concurrent severe illness (Uncontrolled DM, Renal Dysfunction, Liver disease, hyper and hypothyroidism)
- 5. Chronic organic bowel disorders e.g. inflammatory bowel diseases, TB, Diverticular disease etc
- 6. Any previous gastrointestinal surgery

### i. Sample Size:

For our trial, we will take equal sample size for both the groups  $(n_1 = n_2)$ . The sample size is to be determined using the following formula -

Sample size in each group,  $n_1$  = 2  $\sigma^2(Z_\beta + Z\alpha)^2 \, / \, (\mu_1 - \mu_2)^2$ 

Here,

 $Z_{\beta}$ = 0.84 at 80% power

 $Z\alpha = 1.96$  at 95% confidence interval

 $\mu_1$  –  $\mu_2$ = Minimum clinically important difference = 30 %( a minimal clinically significant reduction of 30% is desirable in probiotics group compared to placebo)

 $\sigma$  = Standard deviation = 87.77 (G. Sisson, et al. 2013)

Since there is no such study or trial carried out in Bangladesh, we could not find any reference value of Standard deviation of IBS-QOL or IBS-SSS scale among patients of Bangladesh. Hence we used a recent study (G. Sisson, 2013) to estimate the standard deviation.

The standard deviation found in the G. Sisson, et al. 2013 trial was 13.21 for IBS-QOL scale and 87.77 for IBS-SSL. Our study objectives include both the measures; hence we have considered the higher value of standard deviation so that the sample size is sufficient to cover both objectives.

Sample size in each group,  $n_1 = 2 \times (87.77)^2 \times (0.84 + 1.96)^2 / (30)^2$ 

= 135

Total sample size, n = 270

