### c. Main outcome variables to be studied:

Changes in abdominal pain for primary objective and overall symptom severity score as a secondary objective.

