## Adjustment for non-compliance/cross-over

We also need to consider dropouts and poor adherence in calculating the sample size. It is estimated that around 5%-8% patients in both groups will drop out in different stages of the trial. The adjusted sample size is calculated based on the following formula –

Adjusted sample size,  $n_{adj} = n/(1-c_1-c_2)^2$ 

Here, n = 270

 $c_1$  = Dropout rate in control group = 8%

c2= Dropout rate in control group = 8%

Adjusted sample size,  $n_{adj} = 270 / (1 - .08 - .08)^2$ 

 $= 384 \approx 400$ 

The adjusted sample size in each group = 200

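### The sample-size target is labelled 30% but computed as 30 points on the IBS-SSS total score, and no calculation is given for the primary outcome, abdominal pain

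*Protocol*

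**What the plan says.** **Target and formula.** Section i (Sample Size) uses the usual formula for comparing two means, with 1.96 for alpha and 0.84 for 80% power. It sets the difference at 30%, glossed as "a minimal clinically significant reduction of 30% is desirable in probiotics group compared to placebo". The worked line then divides by 30 squared, with an SD of 87.77, and gives 135 per group and 270 in total. The dropout section ends with "The adjusted sample size in each group = 200".

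**Scales.** The SD comes from one earlier trial, which the protocol cites for two scales: 13.21 for IBS-QOL and 87.77 for the IBS-SSS (printed as IBS-SSL). The section says "Our study objectives include both the measures" and continues "hence we have considered the higher value of standard deviation so that the sample size is sufficient to cover both objectives". The procedures section gives the IBS-SSS total a range of 0 to 500.

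**Outcomes.** Section c ranks them as "Changes in abdominal pain for primary objective and overall symptom severity score as a secondary objective". The first secondary objective is "To assess the effect of probiotics on global symptom severity scores which includes other symptoms of IBS". Neither objectives list mentions quality of life, which appears as an aim only in the Rationale. The Rationale and the Outcome variables section define a responder as a patient whose own pain score improves by at least 30% from baseline.

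**The concern.** The difference and the SD in this formula must be in the same unit. A percentage can be set against an SD in points only after it has been converted with a reference mean, and the protocol gives none. The target that is stated and the target that was used are therefore different quantities.

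The calculation also concerns the total score, which the protocol ranks as secondary, and does not mention pain. If the trial shows no difference in pain, there is no planned target against which to judge that result. A report that repeats the sample-size section would claim 80% power for a 30% reduction, which was never calculated.

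Finally, one difference combined with the larger of two SDs from different scales cannot serve both scales.

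**Working it through.** **Inputs.** From section i: multipliers 1.96 and 0.84 (sum 2.80), SDs 87.77 and 13.21, difference 30. From the dropout section: 200 per arm and 8% dropout. Assumed here: 184 evaluable per arm (200 × 0.92), the reference means, and the control responder rates. Powers are two-sided at 5%, by normal approximation.

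**1. Reproduce the plan's figure.** n = 2 × 87.77² × 2.80² / 30² = 134.2, rounded up to 135 per arm. It reproduces, with 30 taken as points.

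**2. Which scale.** A raw score on a 0-100 item cannot have an SD much above 50, so 87.77 belongs to the 0-500 total. Thirty points is 30/500 = 6% of that range.

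**3. When 30 points equals 30%.** 30/0.30 = 100, so only at a reference mean of 100. For a true 30% reduction with SD 87.77 and 135 per arm:

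| Assumed mean | 30% in points | Power at 135 per arm | Needed per arm for 80% |
|---|---|---|---|
| 75 | 22.5 | 56% | 239 |
| 90 | 27 | 71% | 166 |
| 100 | 30 | 80% | 135 |
| 125 | 37.5 | 94% | 86 |
| 150 | 45 | 98.8% | 60 |
| 175 | 52.5 | 99.8% | 44 |

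The protocol calls totals below 175 mild and sets no minimum severity. The two lowest means are possible, but nothing in the document supports them.

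**4. Total score at the planned size.** Power for 30 points is about 91% at 184 per arm and 92.8% at 200. At 184 the detectable difference is 2.80 × 87.77 × √(2/184) = 25.6 points.

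**5. IBS-QOL.** The same formula with 30 points gives 2 × 13.21² × 2.80² / 30² = 3.04, or 4 per arm. The difference plainly does not carry over between scales. At 184 per arm, 2.80 × 13.21 × √(2/184) = 3.9 points is detectable, so no shortfall is shown, but no IBS-QOL target is stated either.

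**6. Pain as a responder rate.** Two proportions, pooled variance under the null, 184 per arm:

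| Assumed control rate | Detectable at 80% power | Power for 10 points | Power for 15 points |
|---|---|---|---|
| 20% | 12.8 points | 60% | 90% |
| 30% | 14.1 points | 52% | 85% |
| 40% | 14.5 points | 49% | 82% |
| 50% | 14.4 points | 49% | 83% |

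**7. Pain as a mean score or change.** 2.80 × √(2/184) = 0.29 SD. This cannot be turned into points without an SD, and the protocol gives none for pain.

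**The case against.** **The 30% may be the responder threshold.** The Rationale and the Outcome variables section use the same figure. But there it is a change within one patient against baseline, whereas section i makes it a difference between arms and puts it into a means formula. The objection fails.

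**The total score may count as primary.** The second primary objective is "To assess the efficacy of a multi-strain probiotic supplement as a treatment option for IBS", and the research question asks whether the combination is "more effective at reducing IBS symptoms than standard treatment of IBS". Both are loose enough to fit a total score. Section c is not, and the objectives list places global severity among the secondary aims. Even on the loose reading, the 30% label stays wrong and pain still has no calculation.

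**Nothing changes in practice.** The sum is correct, and for any reference mean above 100 the size is more than enough for a true 30%. This stands, and it limits the severity. A reader might infer that the trial is too small. The document does not support that: power falls below 80% at 135 per arm only if the mean is under 100, and nothing points there.

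**Pain is surely covered.** A reader might also infer that a mean pain score is safe because a 0-100 item has an SD of at most about 50. That bound is for a raw score. Section c names changes in pain, and a change on such an item can have an SD of up to 100, at which 2 × 100² × 2.80² / 30² = 174.2, or 175 per arm, would be needed for 30 points. So extreme an SD is unlikely, but no ceiling in points can be stated without an SD. The data sheet also records days with pain, so the pain score need not be a single item.

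**All randomised patients are analysed.** Section q says so, and 184 is therefore an assumption. At 200 per arm the total-score power is slightly higher, as shown above.

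**Conclusion.** The point holds as an error in the stated target and in the outcome it is attached to. The figure of 135 per arm gives 80% power for a 30-point mean difference in the IBS-SSS total, assuming the SD of 87.77 applies. It does not give 80% power for a 30% reduction unless the reference mean is 100, and it says nothing about pain. The claim to cover both scales is unsound, and the quality-of-life objective it relies on is not in the objectives list.

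No underpowering is shown for the total score, IBS-QOL or pain. Power for pain is unstated. If the endpoint is a responder rate, the planned size is reasonable for differences of about 13-15 percentage points and weak for 10 (49-60% power), given control rates of 20-50%, which are assumed. This should be fixed, but it does not put the design in doubt.

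**What to change.** Keep 400 patients and revise the text in four places.

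1. **Target.** Either restate it as a 30-point difference in the IBS-SSS total, with a reason for 30 points (80% power at 135 per arm, about 91% at an assumed 184), or keep 30%, state the reference mean behind it and recompute the power. Either repair is acceptable.
2. **Two scales.** Delete the sentence claiming that the larger SD covers both objectives. If quality of life is an objective, list it and give it its own difference.
3. **Form of the pain endpoint.** Reconcile the passages. The Rationale asks for responder rates and ranks numerical change in scales as secondary, the Outcome variables section defines a responder, and the Abstract plans a Chi-square test; these point to a responder rate. Section c (changes in pain) and section p (unpaired t-test on symptom score) point to a mean score or change.
4. **Detectable difference on pain.** State it at 80% power with its assumption: about 13-15 percentage points for a responder rate, noting the 49-60% power for 10 points; or 0.29 SD for a mean, converted to points only if an SD is given.

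The cost is rewording, with no extra patients. The drawback is that the pain figure depends on an assumed control rate or SD and is worked back from the sample size, not derived from a chosen target. The protocol should say so.
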